This study evaluates the effect of a fractionated carbon dioxide laser on surgical scars of the face and neck over 12 months. Anyone with a surgical scar on the face and neck who has not had laser therapy may be eligible. The visits occur every three months for up to 12 months. Subjects will be randomly assigned to receive two high energy treatments or two low energy treatments. During the study visits, the scars will be photographed pre-treatment and the subject will complete a questionnaire to rate the scar. Three physicians will also evaluate the scar: one as a live assessment and the other two will evaluate the scars after each visit using photographs. Patients will receive their assigned treatment, obtain post-treatment instructions, and a diary to record redness, swelling, pain, itching, or other skin changes after treatment. Patients and raters will be blinded to which therapy level the patient receives until the 9-month visit (Visit #3) at which time patients will be unblinded and offered to have a third high energy treatment if in the high energy treatment group or to have two high energy treatments if in the low energy treatment group.

Study Timeline

The study will occur over 14 months. Our tentative timeline consists of recruitment and screening to occur in November 2016-September 2017. Study visits and data collection would occur between November 2016 and September 2017. Preliminary data analysis and publication of preliminary results would occur between August 2017 and March 2018. Final data analysis and publication would be between October 2018 and January 2019.

Introduction

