prospective cohort study of 20 Chinese women, blinded evaluators and patients agreed at one and three months post-CO2 laser resurfacing that the deep wrinkles on the faces of subjects were more shallow, pores smaller, texture more smooth, and skin appeared brighter compared to the untreated side. Additionally, there was a perpetual decrease in the roughness of treated skin by 9.72% on day 7 post treatment, 18.92% at 1 month follow-up, and 24.40% at 3 months assessed by a 3-D in-vivo imaging system (Hong Li, 2010). Likewise, CO2 laser resurfacing for acne scars yielded similar positive outcomes. Chapas et al performed an unblinded cohort study of 13 patients with moderate to severe acne scarring to evaluate change in acneiform scars following two to three treatments with ablative laser resurfacing with a 30 W CO2 Fraxel re:pair laser. She observed that subjects and investigators rated 26-50% improvement in atrophy and cheek scarring three months after laser treatment. Use of the Phaseshift Rapid In Vivo Measurement (PRIMOS) topographical skin imaging system demonstrated that the mean depths of scars improved by 66.8%. With higher energy levels (70-100 mJ) on deeper scars on the cheek after the second and third treatment, scars improved by 51-75% three months after the final treatment (Chapas et al, 2008). In another study using a cohort of 60 patients with various morphologies of acne scars over three years with 3-4 sessions, a blinded evaluator rated 67% of patients with good-to excellent improvement in their overall appearance compared to images of their pre-treatment status (Majid, 2014).

Our study is a prospective, randomized double-blinded placebo-controlled trial to evaluate the efficacy of fractionated carbon dioxide laser in improving surgical scars on the head and neck. Scar assessments will be based on objective changes identified with the Canfield Vectra M3 3D Imaging System and subjective changes identified with the Patient and Observer Scar Assessment Scale (POSAS), a validated scar scale.

Study Objectives/Primary and Secondary

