The primary objective is to assess the efficacy of fractionated carbon dioxide laser in improving surgical scars. Objective assessment of the scars will involve the Vectra microtopographic imaging system to measure changes in the length of the scar. The Patient and Observer Scar Assessment Scale (POSAS) is a validated survey that will be utilized for subjective assessments of the vascularity, pigmentation, thickness, pliability, surface area, relief, pain, and pruritus.

The secondary objective will be to evaluate the tolerability of the laser, by assessing the severity and duration of known side effects of laser therapy such as erythema, edema, burning sensation, post-inflammatory pigment changes, infection, scarring, xerosis, pruritus, bronzing, and any other adverse events that arise following treatment. Patients will be given a 30-diary after each treatment to document this information.

Selection and Withdrawal of Study Subjects

Study Population

The study population will consist of 50 adult patients 18 years of age or older with surgical scars located on the head and neck.

Minors are not included due to the Mohs patient population being adults only who have undergone surgical excisions of skin cancers on the head or neck. Although participants are not

required to be patients in the Mohs clinic, scars and healing may be significantly different in children, making the data less reliable and difficult to interpret.

Inclusion and Exclusion Criteria

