the subject tends to form keloid scars or scars from minor trauma. Also, the subject should not participate in the study if the subject has taken oral isotretinoin medication within the past 6 months. In addition, the principle investigator may exclude the subject from the study if she determines that the study may put the subject at risk. The subject will provide written consent (permission) to be a participant in the study and for the research team to access the subject's health information to learn more about the surgery that resulted in the scar and the original features of the scar. Immediately before any study visit, the subject will be asked to not wear any make-up or use facial moisturizers (or moisturizers on the neck). The subject will be asked to cleanse their face with a gentle cleanser, such as Cetaphil, provided in the office prior to treatment.

Other procedures at this visit:

- The subject will have photographs taken of the scar that will be shared confidentially with two other research physicians in the study for them to answer questions about the scar.
- The subject will complete a questionnaire about the scar and another research physician will see the subject at this visit to evaluate the scar.

If the subject qualify for study treatment the following may occur at the same visit or at a return visit within 30 days. The following will occur:

- If the subject has a history of recurrent fever blisters/cold sores on the lips or face, The subject will be offered a three day prescription for an antiviral medication that the subject can fill at the subject's pharmacy to prevent a recurrence since laser treatments may increase the chance of recurrent episodes. The subject would take one pill every twelve hours the day prior to treatment, on the treatment day, and the first day post-treatment. The subject or their insurance plan must cover the cost of the medication. This may delay the treatment to a later date within 30 days of the screening visit.
- The subject will complete a pre-treatment questionnaire.
- The subject will receive laser treatment as randomized to either high energy or low energy treatment which includes:
 - Prior to treatment, the subject will be asked to cleanse his or her face with a gentle cleanser, such as Cetaphil, provided in the office in order to remove all lotion, creams, make up, and sunscreen.

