 - Expect the treated area to be red for several weeks. You can use makeup starting three days after the treatment, but it is best to wait until the skin has fully exfoliated and becomes pink to red shiny, smooth skin. This usually takes 7 to 10 days.
 - Some swelling may develop, and generally lasts 1-2 days. It is recommended that you sleep in a slightly elevated position to help relieve swelling.
 - It is common to feel a heat or sunburn sensation in the treated areas. This heat will dissipate over the next few hours. Cold compresses, such as ice, may help soothe the heat and can be gently applied to the skin.
 - Pain is uncommon after the first few days, and usually subsides with Tylenol and cooling the skin. Itching can be seen, and will usually last a few days or less. You can press on the clean itchy skin with a cotton tipped applicator (i.e. Q-tip) to relieve the itching. Avoid scratching the skin.
 - Normal daily activities may be resumed immediately after treatment. Avoid strenuous exercise, bending, straining, stooping or lifting heavy objects for 48 hours. These activities may cause swelling and pain in the treatment area. If a patient is not able to receive the treatment on the same day as the screening and randomization visit (possibly due to an ongoing oral herpetic infection), they may return to the office within 30 days for their first treatment.

Study Visit #2

The subject will be asked to return in 3 months for a second treatment visit with the following activities:

- The subject will complete a pre-treatment questionnaire
- o The subject will receive laser treatment as randomized to high energy or low energy treatment
- The subject will obtain post-treatment instructions
- The subject will obtain a paper diary to record possible reactions such as redness, swelling, pain, itching or color changes following treatment
- If the subject has a history of recurrent fever blisters/cold sores on the lips or face, the subject will be offered a three day prescription for an antiviral medication that the subject can fill at the subject's pharmacy to prevent a recurrence since laser treatments may increase the chance of recurrent episodes. The subject would take one pill every twelve hours the day prior to

treatment, on the treatment day, and the first day post-treatment. The subject or their insurance plan must cover the cost of the medication. This may delay the treatment to a later date within 30 days of the screening visit.

Study Visit #3

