As soon as the PI becomes aware of an AE that meets the criteria for an SAE, the SAE should be documented to the extent that information is available. A report must be submitted by the study site to the SLU IRB, within 24 hours. Forms for reporting SAEs will be provided to the study site. SAEs will be recorded from the time of informed consent, through the end of the study. If in the opinion of the Investigator, an SAE occurring outside the specified time window (i.e., following subject completion or withdrawal from the study), is deemed to be device related, then the event should be reported with 24 hours as outlined above. The Investigator should institute any clinically necessary supplementary investigation of SAE information.

Death

In the case of subject death, any post-mortem findings/reports will be requested and a report (even if a preliminary diagnosis/cause of death is available) will be submitted to the SLU IRB within 24 hours of learning about the death.

Reporting of Pregnancy

In the case of subject pregnancy, the subjects will be discontinued from the study and will be followed leading up to delivery.

Data Analysis and Statistical Considerations

At the completion of the study, the data obtained will be reviewed and analyzed with the aid of the Saint Louis University Center for Health Outcomes Research. A chi-square test along with the Wilcoxon signed rank test will be performed to assess significant difference between clinical improvement scores between study visits. There is no data to suggest that there is a difference in the appearance of older (more than 1 year old from the initial injury) and newer scars post-therapy. We will aim to recruit 20 patients with old scars (10 of which will be in the high energy treatment group, and 10 of which will be in the low energy treatment group). In terms of statistical analysis, we will review whether there is a difference between the post-treatment measurements and appearance of older scars and newer scars.

Quality Control and Quality Assurance

Quality control and assurance for this study will be performed by an internal review every 3 months to ensure that the data collected is in accordance with the goals of this study and to address any issues with data collection or performance of any study procedures.

Direct Access, Data Handling and Record Keeping

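### Labelled placebo-controlled with laser efficacy as the aim, but both arms receive active laser and no high- versus low-energy test is stated

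*Combined protocol and SAP*

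**What the plan says.** - **Design label (Introduction):** "Our study is a prospective, randomized double-blinded placebo-controlled trial to evaluate the efficacy of fractionated carbon dioxide laser".
- **Primary objective (Study Objectives/Primary and Secondary):** "The primary objective is to assess the efficacy of fractionated carbon dioxide laser in improving surgical scars".
- **Arms (opening study summary):** "Subjects will be randomly assigned to receive two high energy treatments or two low energy treatments". Dose Regimen defines high energy as the Mid mode (45-257 mJ) or the Deep mode (30-70 mJ), and low energy as the Light mode (18-74.5 mJ).
- **Treatment given (Study Visit #1):** "The subject will receive laser treatment as randomized to either high energy or low energy treatment". Study Visit #2 repeats this.
- **Analysis (Data Analysis and Statistical Considerations):** "A chi-square test along with the Wilcoxon signed rank test will be performed to assess significant difference between clinical improvement scores between study visits". The only other comparison there is by scar age: "we will review whether there is a difference between the post-treatment measurements and appearance of older scars and newer scars".
- **Nearest hint of an arm comparison (Study Procedures):** a remark that the schedule lets all subjects be compared after two treatments. It names no arms, endpoint or test.
- **Attribution of change (Inclusion and Exclusion Criteria):** change in scars of 52 weeks or more may be presumed to come from the laser. The protocol concedes that no confirmed findings support this. Scars of 8 to 51 weeks are also eligible.

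**The concern.** The label and the primary objective promise an answer about laser against no laser. With laser in both arms, randomisation supports only a comparison of energy modes. The stated tests do not use that comparison: the signed rank test is paired, and both tests are described as being between visits.

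Followed literally, the plan would present improvement from baseline as efficacy. In younger scars, improvement from treatment cannot be told apart from natural maturation. The between-arm contrast avoids this problem in expectation, because maturation should act equally in both arms, but it has no stated test.

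The interpretation would also be limited. High energy better than low would be indirect, dose-response evidence that the laser works. Similar improvement in both arms could neither show nor refute efficacy against no laser.

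**Working it through.** The plan gives 50 subjects but no alpha, power, effect size, SD or dropout rate, so it has no calculation to reproduce. The check has three parts.

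**1. Text set side by side**

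| Element | What the plan gives | Laser-free control? | High vs low? |
|---|---|---|---|
| Randomised arms | High energy; low energy | No (0 of 2) | Yes, by design |
| Chi-square test | Between study visits | No | Not stated |
| Wilcoxon signed rank test | Between study visits | No | No (paired) |
| Older vs newer scars | A review, no test named | No (all are treated) | No |

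No arm is free of laser, and none of the named analyses is stated to compare the arms.

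**2. How far between-visit tests can mislead**

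The recruitment aim is 20 older scars among 50 subjects. If it is met exactly (an assumption), 50 - 20 = 30 subjects, or 30/50 = 60%, fall outside the presumption that change is due to the laser.

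Illustration, 20,000 simulated trials: normal change scores with SD 1; 25 per arm (15 younger and 10 older scars in each); no laser effect in either arm; a maturation shift m in younger scars only. The mean shift over all 50 is then 0.6 × m. The documents give no value for m, so a range is shown, in SD of the change score. Entries are the share of trials with p < 0.05.

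| m | Mean shift, all 50 | Signed rank, all 50 | Signed rank, one arm of 25 | Between arms, adjusted for scar-age group |
|---|---|---|---|---|
| 0 | 0 | 5.1% | 5.0% | 5.1% |
| 0.2 | 0.12 | 12.6% | 8.0% | 5.0% |
| 0.3 | 0.18 | 22.7% | 13.1% | 5.0% |
| 0.5 | 0.30 | 51.1% | 26.8% | 4.9% |
| 0.8 | 0.48 | 87.4% | 54.9% | 5.0% |

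If all 50 scars shift by 0.3, 0.5 or 0.8 SD (3,000 trials), the signed rank test on all 50 is significant in 52%, 92% or 100%. The table is the milder scenario. The last column stays near 5% because both arms are given the same shift, which is what randomisation provides in expectation.

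**3. What the between-arm comparison could detect**

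Assumptions: equal allocation, no dropout, two-sided alpha 0.05, 80% power, two-sample t-test. Adjusting for a baseline score with correlation r to the Visit 3 score multiplies the detectable difference d by √(1 - r²). Values are in SD of the Visit 3 score, a different scale from the change-score SD in part 2.

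| Per arm | Unadjusted d | r = 0.3 | r = 0.5 | r = 0.7 |
|---|---|---|---|---|
| 25 | 0.809 | 0.771 | 0.700 | 0.578 |
| 20 | 0.909 | 0.867 | 0.787 | 0.649 |

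Example: 0.809 × √(1 - 0.25) = 0.700.

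**The case against.** The strongest reply is that an arm comparison is plainly intended and merely unwritten. The chi-square test is ordinarily for independent groups, the older-scar target is split 10 and 10 by arm, evaluators are blinded to energy level until Visit 3, and the schedule is said to allow comparison after two treatments. That makes intent plausible. It does not supply an analysis: no text names the contrast, endpoint or test, and the stated purpose of both tests is change between visits.

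A second reply is that the placebo label is one word and misdirects no procedure, and that a low-energy comparator is a legitimate choice. Both points are fair, and the design need not change. But the primary objective repeats the efficacy claim, so the problem is not confined to the label.

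Third, the error rates depend on assumed maturation, normal scores and one pooled test that the plan does not specify. This is correct. They show the direction and possible size of the problem and do not predict this trial.

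Fourth, balance holds only in expectation. The section on assigning subjects describes a spreadsheet prepared by the investigator and no random sequence. A two-level scar-age adjustment cannot remove chance imbalance within 8 to 51 weeks. This limits the proposed analysis, but it remains better protected than before-after change.

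**Conclusion.** The concern holds and should be corrected. Neither arm is laser-free, so the placebo label is wrong and the primary objective asks a question that the randomisation cannot answer. The comparison it can answer has no stated test. These conclusions come from the text and need no assumption.

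The size of the risk does rest on assumptions. With exactly 20 older scars, 60% of subjects lie outside the protocol's own hedged presumption. With no laser effect and maturation of 0.2 to 0.8 SD of the change score in those subjects, a pooled between-visit test would be significant in 13% to 87% of trials.

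A secondary point: the Deep energy range lies inside the Light range, and no rule is given for choosing Mid or Deep or the energy within a mode. The arms are still separated by named device mode, so this does not show that they are alike.

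**What to change.** 1. Delete the placebo-controlled label. Restate the primary objective, and any conclusion, as high- versus low-energy treatment.
2. Make the primary analysis a between-arm comparison at Visit 3, defined as 3 months after the second treatment, with ratings completed before unblinding and before any optional treatment. Anchor it to the second treatment because the study summary calls Visit 3 the 9-month visit, while the visit schedule puts it about 3 + 3 = 6 months after the first treatment.
3. Name one score. One option is the total observer POSAS from the blinded live rater, one of the three physician raters. Adjust for baseline score and scar-age group, and report a confidence interval.
4. Keep the between-visit tests and the older-versus-newer review as supportive, and state that they are not evidence against no laser.
5. Secondary: log mode and settings at each session and tabulate them by arm.

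The cost is protocol wording, one analysis of data already collected and a few treatment-log fields. No patients, visits or arms are added. The claim becomes narrower and precision is limited (about 0.81 SD unadjusted with 25 per arm, 0.91 SD with 20), so a null result must be read from its confidence interval.

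### The primary objective has no single primary endpoint, rater, time point, between-arm comparison or alpha, so any one significant result could be reported as efficacy.

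*Combined protocol and SAP*

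**What the plan says.** Study Objectives/Primary and Secondary opens with a general aim: "The primary objective is to assess the efficacy of fractionated carbon dioxide laser in improving surgical scars". Two instruments follow. One is the "Vectra microtopographic imaging system to measure changes in the length of the scar". The other is POSAS, used for "subjective assessments of the vascularity, pigmentation, thickness, pliability, surface area, relief, pain, and pruritus". The eight attributes are not ranked, and no total score is defined.

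On raters, the opening summary says that "the subject will complete a questionnaire to rate the scar" and that "Three physicians will also evaluate the scar", "one as a live assessment and the other two will evaluate the scars after each visit using photographs". No rule says whose rating counts or how ratings are combined.

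On timing, the same summary says "The visits occur every three months for up to 12 months". Study Procedures remarks that the design lets all subjects be compared after two treatments, but neither the objectives nor the analysis section makes that comparison primary.

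In Data Analysis and Statistical Considerations, the tests named are a chi-square test and a Wilcoxon signed rank test, which "will be performed to assess significant difference between clinical improvement scores between study visits". The only other planned analysis is a review of older against newer scars. No alpha, sidedness, outcome hierarchy or multiplicity adjustment is given anywhere.

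**The concern.** Nothing in the plan says which result decides whether the laser worked. The quantity to be tested could be a single attribute, a POSAS total, a photograph rating or a responder category. It could come from any of four raters and from more than one visit. The named comparison is between visits, not between the randomized arms, although the trial is described as randomized, double-blind and placebo-controlled.

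An analyst could therefore report whichever attribute, rater, visit or test reached significance as meeting the primary objective, without departing from the protocol. The error rate behind such a claim would exceed the nominal level by an amount nobody could state afterwards, because the set of tests was never fixed.

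**Working it through.** The plan gives no alpha, power or error rate, so it has no figure of its own to reproduce. The check asks how the false-positive chance depends on what is counted as tested.

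**Inputs from the documents**
- Scar length by Vectra: 1 outcome (Study Objectives). It is an imaging measurement, not a rater's score.
- POSAS attributes: 8 (Study Objectives).
- POSAS raters: 1 patient and 3 physicians = 4 (opening summary).
- Follow-up visits in the randomized period: Visits 2 and 3. Visits 4 and 5 follow optional, unblinded treatment.

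**Assumptions not in the documents**
- Each test is two-sided at 5% and unadjusted.
- No outcome has a true effect (global null).
- Test statistics are normal, with a common pairwise correlation ρ between 0 and 0.7.

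**Formulas**
- Independent tests: P(at least one) = 1 − 0.95^k.
- Correlated tests: P = 1 − E{[Φ((1.96 − √ρ·U)/√(1−ρ)) − Φ((−1.96 − √ρ·U)/√(1−ρ))]^k}, with U standard normal. Numerical integration and simulation agree.

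**Results**

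| What is tested | k | ρ = 0 | ρ = 0.3 | ρ = 0.5 | ρ = 0.7 |
|---|---|---|---|---|---|
| One POSAS total and length | 2 | 9.8% | 9.5% | 9.1% | 8.4% |
| Patient total, observer total and length | 3 | 14.3% | 13.6% | 12.5% | 10.9% |
| Eight attributes and length, one rater, one visit | 9 | 37.0% | 32.6% | 26.9% | 20.2% |

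The first column is 1 − 0.95² = 0.0975, 1 − 0.95³ = 0.1426 and 1 − 0.95⁹ = 0.3698.

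**Illustration only: raters and visits tested separately**
- Four raters at one visit: 8 × 4 + 1 = 33 tests. The chance is 82% if independent and 35% at ρ = 0.7.
- Four raters at two visits: 2 × 33 = 66 tests. The chance is 97% if independent and 44% at ρ = 0.7.

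These two counts assume that every rater scores all eight attributes. The second also assumes that Visit 2 is fully scored. The opening summary and Study Procedures point to photographs and an evaluation at that visit, but the Study Visit #2 list shows only a questionnaire.

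**The case against.** The strongest reply is that separate testing of nine outcomes is inferred. The objectives list what POSAS covers; they do not say each item will be tested. The Introduction names two instruments, and the analysis section speaks only of scores. If a POSAS total and length are what is meant, the inflation is modest, at 8–10%. This stands, and it is why the range starts there. The documents do not settle which reading applies, and that is itself the defect.

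A reader might also infer that a chance finding is likely, meaning more probable than not. The documents do not support that. Nine tests give 20–37%. Passing one half needs at least 14 independent tests, or separate analysis by rater and visit, which the plan does not state. Two of the physicians work only from photographs, while the attributes include pain, pruritus and pliability, so multiplying attributes by raters is partly assumption.

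A third reply is that a global null fits poorly with paired tests between visits. Scars may enter at eight weeks, and the protocol says most are mature only at one year, so both arms may change without any laser effect. This also stands. It means the percentages describe tests for which no true difference exists, such as a comparison of equivalent arms. Reading change over time as efficacy is a separate problem, and it strengthens the case for naming a between-arm comparison.

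Finally, Visit 3 is evidently the intended time point: it follows two treatments, and subjects are unblinded there. That is fair, but the analysis section does not say so.

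**Conclusion.** The concern holds as a failure to designate. No endpoint, rater, time point, between-arm comparison, alpha or multiplicity rule is primary, and the tested score is undefined. Nothing elsewhere in the document repairs this.

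The false-positive chance is about 8–10% on the narrowest reading and about 20–37% when length and each attribute are tested once. Both ranges rest on an assumed two-sided 5%, a global null and correlations from 0.7 down to independence. Separate tests by rater and visit would raise the figure by an amount the documents leave open. The finding supports neither a single error rate nor a claim that a spurious result is more likely than not.

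**What to change.** Amend Study Objectives and Data Analysis and Statistical Considerations before unblinding. Subjects are unblinded one by one at Visit 3, so this means before the first subject reaches that visit.

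- **Primary endpoint.** Name one score from data already collected, at Visit 3, compared high versus low energy, adjusted for the baseline value, at a stated two-sided 5%. The observer POSAS total from the blinded live rater is a reasonable choice. The documents do not compel it, and the sponsor may prefer another single score and rater. Whichever is chosen, state which items make up the total and how they are summed.
- **Time point.** Define it as three months after the second treatment, before any optional treatment. The opening summary calls Visit 3 the 9-month visit, but two three-month intervals give 3 + 3 = 6 months.
- **Tested quantity.** Replace clinical improvement scores with the named endpoint.
- **Other outcomes.** If the observer total is primary, make the patient POSAS total and Vectra length secondary with a stated adjustment such as Holm. Report single attributes, other raters and other visits descriptively.

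With one primary test the error rate is 5% by construction. Keeping nine co-equal outcomes would instead need about 0.05/9 = 0.0056 per test under Bonferroni. The change needs protocol and SAP wording but no new visits, procedures or patients. The downside is that fewer outcomes can be called significant. It does not supply a power basis for the 50 patients, which the documents also lack.
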